### **M. STATISTICAL METHODS**

Descriptive statistics will be used to assess **feasibility** of AT. Regarding **preliminary efficacy** of AT, we will use log-binomial regression with an intent-to-treat approach (i.e., missing=smoking) to compare the effect of the treatment on the dichotomous abstinence outcome at 12 weeks post-enrollment, controlling for selected covariates such as sex, education level, and/or baseline stress level. Secondary outcomes will be examined using appropriate linear and generalized linear mixed models with log-binomial and linear regression for binary and continuous variables, respectively. Given the preliminary nature of the RCT, we do not expect to have sufficient power for full hypothesis testing. However, from our previous work, we anticipate that the abstinence at the 12-week follow-up will be 8% in the SC group. With 40 participants in each group, we will have 80% power to detect a difference as small as 20% in

smoking abstinence rates between groups ( $\alpha=0.05$ , one-tailed, unadjusted).

**Mixed methods data analysis.** At the 3-month follow up assessment, we will use additional open-ended questions at the end of the assessment to explore why and how the participants did or did not successfully quit smoking and stay abstinent. Specifically, for participants who were biochemically confirmed abstinent, the questions will focus on what motivated them to quit and how they overcame challenges or barriers to stay abstinent. For participants who were not abstinent, the questions will focus on why they did not or could not quit, what they underwent, what challenges or barriers they had, and what would help them quit in the future.

Two research team members will perform qualitative data coding with the aid of the R-QDA. Discrepancies will be discussed to achieve intercoder agreement. Codes and quotations will be arranged into focused themes (i.e., thematic content analysis) to develop the mixed methods data inventory. Next, we will examine quantitative (RCT) and qualitative data jointly, using the *integration strategy of explaining* with the intent to explore why participants could or could not quit and stay abstinent. Mixed methods linked data, results, and meta-inferences will be presented in visual joint displays, similar to our previous publication.

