### Abstract

In Lao People's Democratic Republic (Lao PDR), tobacco smoking prevalence among cancer patients is high: 60% in men and 15% in women. Evidence from developed countries suggests that smoking cessation offers considerable benefits for cancer survivors, including improving cancer treatment outcomes, reducing recurrence rates, reducing second primary tumor development, and reducing overall cancer mortality rates. Despite, ***no tobacco treatment programs are available*** in major (public) hospitals in Lao PDR, including in cancer hospitals/institutions. The parent project (1R21CA253600-01, **OUHSC IRB#: 12189**) aims to adapt and evaluate the efficacy of our theoretically and empirically based mobile health (mHealth) technology to help Lao general patients quit smoking cigarettes. This mHealth automated treatment (AT) approach includes a fully automated, interactive, personalized, smartphone-based intervention for behavioral treatment, delivered through our Insight platform. In year 1 of the parent project, we have been adapting our intervention content to the sociocultural context, language, and communication styles of Laotians. The ***purpose*** of this supplementary project is to expand our mHealth-based AT to ***address the pressing need for smoking cessation among cancer survivors and their caregivers in Lao PDR***. In this project, we will adapt our intervention and materials to make them comprehensible and relevant to these target populations. Next, we will conduct a pilot randomized controlled trial (RCT, N=80) to evaluate the preliminary efficacy of the intervention. Cancer survivors (n=40) and caregivers (n=40) of both sexes who smoke will be recruited at Setthathirath Hospital and Lao National Cancer Center. Similar to the parent project's design, participants will be randomized to 1 of 2 treatment groups: standard care (SC) or AT (20 cancer survivors and 20 caregivers in each group). SC consists of brief advice to quit smoking, self-help written materials, and a 2-week supply of NRT (transdermal patches). AT consists of all SC components plus our fully-automated interactive smartphone-based treatment program, personalized and tailored to cancer survivors or caregivers. The ***primary RCT outcome*** is biochemically confirmed self-reported 7-day point prevalence abstinence at 3 months post-study enrollment. The ***specific aims*** are: 1) to evaluate the feasibility of AT in cancer survivors

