and caregivers, and 2) to evaluate the preliminary efficacy of AT in each cancer survivor/caregiver subgroup.

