### A. SPECIFIC AIMS

The specific aims are to:

- **Aim 1:** Evaluate the feasibility of AT in cancer survivors and caregivers. *Hypothesis (H1):*  $\geq 75\%$  of AT content will be viewed/opened as indicated by digital date/time stamp in Insight.
- **Aim 2:** Evaluate the preliminary efficacy of AT in each cancer survivor/caregiver subgroup. *Hypothesis (H2):* At the 12-week follow-up, 7-day point prevalence abstinence will be higher in the AT (vs. SC) group.
- **Aim 3 (capacity building):** Advance mHealth research capacity in Lao PDR and sustain the US-Lao PDR research network by supporting Lao investigators through in-person workshops, in-service trainings, online trainings, manuscript preparation, and future mHealth research collaboration and grant applications.

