This supplementary project is **relevant and responsive** to the NOSI [NOT-CA-21-058](#) because it focuses on stimulating global cancer survivorship research using mHealth in Lao PDR—a LMIC as defined by the World Bank. Specifically, this study will evaluate the feasibility of a care/intervention delivery model beyond healthcare settings (i.e., mHealth approach) for cancer survivors (6,000 new cancer cases each year, the most common types: liver, breast, lung, and cervical-uterine) and caregivers. The study will adapt an evidence-based survivorship care service (i.e., smartphone-based smoking cessation treatment) in the United States (US) to serve these populations. This application is built on and leverages our existing relationships with stakeholders at national institutions in Lao PDR, including Setthathirath Hospital (SH), Lao

National Cancer Center (LNCC), National Tobacco Control Committee (NTCC), and the Ministry of Health (MOH). Results from this pilot project will be critical for developing our future R01 application and will contribute **significantly to reducing tobacco-related complications in cancer treatments, co-morbidities, cancer recurrence, and mortality rates in cancer survivors.**

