## C2. PRELIMINARY STUDIES

Most relevant to this proposal is our most recent pilot work (with qualitative and quantitative

components) at an HIV clinic in Phnom Penh, Cambodia. We linguistically and culturally adapted the intervention for Cambodian smokers, and then conducted a pilot RCT comparing SC (n=25) to AT (n=25) delivered by our Insight™ platform. Of all scheduled notifications and weekly assessments during the 2-month treatment period, 75% were delivered properly (i.e., the phones were properly charged, turned on, and not lost). Of all delivered messages and assessments, 81% were opened, as indicated by the digital date/time stamp. Retention through the end of the 2-month treatment period, as indicated by returning to the clinic for biochemical confirmation of smoking status (expired CO) was very promising – 100% in the AT group and 92% in the SC group. The **biochemically verified 7-day point prevalence abstinence rate at 2 months was 40% in the AT group and 8% in the SC group** (RR=5.0; 95% CI: 1.2–20.5). The AT group also scored significantly better (p=0.001) on knowledge items about smoking-related health risks and had a greater, but nonsignificant, change in cessation self-efficacy. Most participants agreed that the AT program was helpful in supporting smoking cessation (92%) and would recommend it to other smokers (88%). These data demonstrate the **acceptability, feasibility, reliability, simplicity, and preliminary efficacy of our AT technology in LMICs**. This success suggests that **AT may be appropriate and efficacious in Lao PDR**, a culture comparable to Cambodia.

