**Figure: Study schema**

With these criteria in our Cambodian pilot study, we recruited 2–5 participants per day; thus, we expect a similarly high consent rate and feasibility for this study.

**Baseline assessment.** Enrolled participants will complete a 45-minute baseline self- or assisted interview, managed and delivered by REDCap. Participants will be randomly assigned to SC or AT by the REDCap randomization module (simple, 1:1). Smartphones will be loaned to participants as needed. All participants will complete a brief training session on smartphone use and the Insight app. The Insight app also includes a help button for instructions on how to use each feature, which participants can review at any time.

**Treatment groups.** SC consists of brief advice to quit smoking delivered by research staff, self-help written materials (the WHO’s “A guide for tobacco users to quit” that we have translated to and validated in Lao), and a 2-week supply of NRT (transdermal patches). AT consists of all SC components plus a fully automated smartphone-based JITAI that involves proactive, interactive, and personalized messages, images, or videos in Lao. Adapted from the parent study and based on the PBM, AT content is designed to increase motivation, self-efficacy, and use of coping skills and reduce nicotine withdrawal symptoms and stress. AT will begin immediately after enrollment and continue for 12 weeks (about 2 messages/images/videos per day, delivered at participants’ preferred time). Quit date is set at day 14 post-enrollment for AT and SC participants. JITAI content for AT participants each week will be **personalized and tailored** to each participant’s **baseline information** (e.g., sex, cancer types, caregiver status, and current health conditions), **current PBM phase**, and **responses to the brief weekly EMAs** that drive AT (see *Measures*). Our AT only targets cigarette smoking because it is the most common type of tobacco used by Lao smokers (95%).

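### Aim 2 asks for efficacy in survivors and in caregivers, but the analysis plan gives only one AT versus SC comparison; its 80% power is for both populations together and falls to about 50% in each

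*Combined protocol and SAP*

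**What the plan says.** The Abstract gives the second aim as "to evaluate the preliminary efficacy of AT in each cancer survivor/caregiver subgroup", and Section A repeats it as Aim 2. The hypothesis attached to that aim, H2, says only that at 12 weeks "7-day point prevalence abstinence will be higher in the AT (vs. SC) group".

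Section M plans a log-binomial regression of 12-week abstinence on treatment, with missing outcomes counted as smoking. The example covariates are sex, education and baseline stress. Survivor/caregiver status is not among them, and no subgroup estimate or treatment-by-subgroup term appears. The Data analysis text in Section D (Stage 2) is the same; its power sentences are printed after the Trial Assessments table.

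On power, Section M first says that power for full hypothesis testing is not expected to be sufficient. It then assumes 8% abstinence under SC and states: "With 40 participants in each group, we will have 80% power to detect a difference as small as 20"%, one-tailed at 0.05, unadjusted. The Abstract gives the make-up of each arm as "20 cancer survivors and 20 caregivers in each group". Section D (Baseline assessment) specifies simple 1:1 randomization and mentions no stratification.

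**The concern.** The aim concerns two populations, while the hypothesis, the model and the power figure concern one comparison across both. Followed as written, Section M yields one overall estimate. The subgroup part of Aim 2 is then either left unanswered or answered by a method chosen after the data are seen.

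A reader who has just met an aim worded by subgroup can also take the 80% as applying to it. The sentence that introduces the power calculation opens with a contrast to the caveat before it, and nothing says the 80% covers survivors and caregivers together.

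This matters because Section B1 says "Results from this pilot project will be critical for developing our future R01 application". With half the stated power in play, an analyst who tests each subgroup separately could easily find a result in one and not the other, and carry that contrast into the design of the next trial.

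**Working it through.** **Inputs.** SC abstinence 8%, a 20-point gain (so AT 28%), one-tailed α = 0.05 (z = 1.645) and 40 per arm, all from Section M. Per subgroup, 20 per arm, from the Abstract. Missing counts as smoking, so everyone randomized is analysed and no dropout adjustment is needed.

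**Formulas**, with n per arm, p₀ = 0.08, p₁ = 0.28 and mean p̄ = 0.18:
- SE = √[(0.08×0.92 + 0.28×0.72)/n] = √(0.2752/n)
- Pooled test: power = Φ{[0.20 − 1.645×√(2×0.18×0.82/n)]/SE}
- Unpooled test: power = Φ{0.20/SE − 1.645}

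**The plan's own figure, 40 versus 40.** SE = 0.0830.
- Pooled: (0.20 − 1.645×0.0859)/0.0830 = 0.71, power 76.0%.
- Unpooled: 2.411 − 1.645 = 0.77, power 77.8%.
- Full enumeration of the two binomials: 77.9% (pooled) and 79.7% (unpooled), with null rejection rates of 5.8% and 6.0%. Fisher's exact test gives 68.8%.

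The stated 80% is at the favourable end of this range and is accepted. It needs 40 per arm, so it is the combined comparison.

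**Each subgroup, 20 versus 20.** SE = 0.1173.
- Pooled: (0.20 − 1.645×0.1215)/0.1173 = 0.001, power 50.1%.
- Unpooled: 1.705 − 1.645 = 0.060, power 52.4%.
- Enumeration: 52.2% for both tests, with a null rejection rate of 4.6%. Fisher's exact test gives 35.6%.

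| | Combined, 40 vs 40 | Subgroup, 20 vs 20 |
|---|---|---|
| Power, 8% vs 28% | 76–80% | 50–52% |
| Power, Fisher | 69% | 36% |
| Difference for 80% power | 20–21 points | 31–33 points |
| 95% half-width (1.96 × SE) | 16 points | 23 points |

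**Sensitivity.**
- SC rate assumed at 5% or 15%, same 20-point gain: subgroup power is 55–59% or 42–45%.
- The earlier pilot's rates, 40% versus 8% (Section C2): subgroup power is 78–82%, Fisher 70%.
- Simple randomization of 40 people gives exactly 20/20 with probability 0.125, and 14 to 26 per arm in 95% of allocations. Averaged over the possible splits, power is 49–54%, Fisher 34%.

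**If the subgroups were tested separately.** With a true 20-point gain in both and about 50% power in each, exactly one would be significant with probability 2 × 0.50 × 0.50 = 0.50.

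**If the risk-ratio model were fitted within a subgroup.** The chance of no quitters among 20 SC participants is 0.92²⁰ = 0.19, and the risk ratio then has no finite estimate. At SC rates of 5% and 15% the chance is 0.95²⁰ = 0.36 and 0.85²⁰ = 0.04.

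**The case against.** The strongest reply is that this is a pilot which calls its efficacy results preliminary and says outright that it lacks power for full testing. A pilot need not power its subgroups. That is fair, and it is why low subgroup power is not the main defect. The caveat does not supply the missing analysis, though, and a number follows it without its scope.

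It can also be said that the 80% is already scoped, since the Abstract shows that 40 per arm means both populations. A careful reader can work that out, so the label is a clarification and not a correction. Likewise, H2 sits under a subgroup-worded aim and could be read as applying within each, and the covariate list is open-ended. But if H2 is meant within each subgroup, the 40-per-arm power figure does not match it. A covariate would adjust the overall effect without giving one for each subgroup.

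The 20-point gain is the detectable difference, not a predicted effect. Section C2 reports that the earlier "abstinence rate at 2 months was 40% in the AT group and 8% in the SC group", and at those rates a subgroup would have close to 80% power. That pilot had 25 per arm, enrolled people from an HIV clinic in another country, measured abstinence at 2 months, and gave a risk ratio interval of 1.2 to 20.5. It is a favourable case and a weak basis for planning.

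Finally, the discordant-results and infinite-risk-ratio problems arise only if someone tests or models the subgroups separately, which the plan does not propose. They stand as consequences of leaving the method open, not as faults in a planned analysis. The simple-randomization point shifts average power very little.

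**Conclusion.** The concern holds. The main defect is that one stated aim has no matching analysis: Aim 2 is about each subgroup, and Section M produces only an overall AT versus SC effect. The secondary defect is that the sole power figure is given without saying it covers both populations; within each subgroup it drops by roughly 25 to 30 points. The stated 80% is not an arithmetic error.

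The size rests on the plan's 8% SC rate, a 20-point absolute gain, a one-tailed 0.05 test and the intended 20 per arm. Across SC rates of 5% to 15% the conclusion is unchanged. It would change only if the true effect were near the earlier pilot's 32 points (40% − 8%). The plan should be amended on this point, but the trial's design is not put in doubt.

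**What to change.** In Section M, and identically in the Data analysis and power text of Section D:

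1. State that the 80% is for all participants combined (planned 40 AT versus 40 SC), and add that within each subgroup (planned 20 versus 20) power for the same difference is about 50%.
2. Name the combined AT versus SC model, with a survivor/caregiver term, as the main test of H2.
3. For the subgroup part of Aim 2, report the AT minus SC risk difference in survivors and in caregivers, each with an exact or score-based 95% interval, described without significance claims.

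The risk difference is a choice; the documents do not require it. Its advantage is that it can still be estimated when an SC subgroup has no quitters: 6/20 versus 0/20 gives +30 points, Newcombe 95% interval 8 to 52.

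The cost is three or four sentences, with no change to sample size or visits. The price is that neither subgroup can carry a significance claim.

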## N. DATA AND SAFETY MONITORING PLAN

The PI ([name]) and site PI ([name]) will be responsible for all data monitoring and for compliance with all federal, OUHSC IRB, and Lao IRB policies and procedures regarding monitoring progress, safety, reporting of unanticipated problems or adverse events, and assuring that actions resulting in suspension of the study are reported.

### ***Unanticipated problems***

The PI will inform the OUHSC and Lao IRB within five (5) business days of discovering any unanticipated problems (both internal and external) involving risks to participants and others.

### ***Serious adverse events***

A serious adverse event is defined as follows: death, a life-threatening adverse event, inpatient hospitalization or prolongation of existing hospitalization, a persistent or significant disability/incapacity, a congenital anomaly/birth defect, or a medically significant event. Risks of participation will be continually monitored and appropriate measures implemented in cases of unforeseen adverse events. If a serious adverse event occurs, the PI will notify the IRB and the designated program person at the NCI in writing. These events will be reported regardless of whether they appear to be related to study procedures.

Given the non-invasive, minimal risk nature of the proposed research, we anticipate no serious adverse events related to the interventions or the study procedures. The types of adverse experiences that may occur, if any, will focus on the possible distress associated with self-interviews during data collection or on the use of nicotine patches. We have included procedures to minimize these risks (see section K above).

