**Measures (Table).** **Primary assessments** will be conducted at **baseline and at the 12-week follow-up**, which collect 3 types of data: self-reported data collected by REDCap, expired air carbon monoxide (assessed with Vitalograph BreathCO) to verify smoking status biochemically, and medical record data (for AT personalization). Most of these measures are similar to the parent study and have been translated into Lao. Participants will be compensated US\$15 after completing each of the two primary assessments.

Participants in both groups will be asked to complete **brief weekly assessments** (EMAs)

via Insight app. AT participants will receive 6 PBM-based smoking-related questions (*Table*) that drive JITAI. To balance the effects of these weekly contacts between the RCT groups, we will ask SC participants to complete a weekly 6-item diet EMA. All participants will be provided a prepaid 3-month unlimited data plan. The **primary outcome** is biochemically confirmed (CO level <6 ppm) self-reported 7-day point prevalence abstinence.

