**Table. Trial Assessments**

Variable type	Measure	BL	W*	12
Descriptors/ potential moderators	Demographics; Health Literacy 	X		X #
	Alcohol and Drug Use 	X		X
	COVID-19–related issues,  co-morbidities 	X		X
	Dependence – Heaviness of Smoking Index 	X		
Feasibility/ Adherence to AT app	Numbers of messages/images/videos opened and completed; weekly assessments opened and completed; activity logs	Date/time stamps in Insight		
Phase-Based Model mechanisms	Wisconsin Smoking Withdrawal Scale 	X		X
	Reasons for Quitting (Intrinsic, Extrinsic) 	X		X
	Contemplation Ladder 	X	X	X
	Kessler Psychological Distress Scale (K10) 	X	X #	X
	Positive and Negative Affect Schedule 	X	X #	X
	Self-Efficacy (related to smoking cessation) 	X	X #	X
Cancer survivorship	Fear of cancer recurrence (survivors only),  family support,  and spiritual well-being 	X		X
Qualitative, open-ended assessment	An in-app participant-initiated assessment—“Share with us anything on your mind”—with an open text field to capture the participant’s thoughts, feelings, and behaviors	Initiated anytime by participant		
Primary outcome	Smoking status in the past week 	X	X #	X
	Expired carbon monoxide at follow-up 	X	X	X
Secondary outcomes	E.g., number of quit attempts, days abstinent, and other tobacco product use 	X		X

Abbreviations: AT, automated treatment; BL, baseline; W, weekly; 12, 12-week follow-up. \**Delivered via Insight app*; \*\**Brief versions of the scales*.

preliminary nature of the RCT, we do not expect to have sufficient power for full hypothesis testing. However, from our previous work, we anticipate that the abstinence at the 12-week follow-up will be 8% in the SC group. With 40 participants in each group, we will have 80% power to detect a difference as small as 20% in smoking abstinence rates between groups ( $\alpha=0.05$ , one-tailed, unadjusted).

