**Protection against Assessment-Related or Intervention-Related Discomfort:**

The potential for discomfort associated with being asked personal questions regarding sensitive topics will be minimized in the following ways:

- Participants will be informed of the nature of questions to be asked and topics covered; participants can decline participation if such topic areas are known to be personally uncomfortable.
- Only measures that have been validated or used in prior studies will be used or will be adapted for use in this study. None of the proposed instruments have been known to evoke serious emotional reactivity.

- The use of self-administration for the assessments on a tablet or phone may help participants feel more comfortable in answering sensitive questions.
- Participants can refuse to answer any questions that they do not wish to answer.
- Participants who become distressed by answering questions will be given resources to access help.
- Participants will be reminded during the consent process that they may contact the research staff with any questions or concerns that arise during their participation.
- Participants may choose to discontinue participation at any time.

Those who experience a skin reaction from nicotine patch use will be instructed to move the site of the nicotine patch each day. Additionally, participants will be instructed to wait at least 7 days before using the same site for patch placement. To minimize nausea, participants will be instructed not to smoke while using the patch. If smoking relapse occurs, the participant will be instructed to stop using the patch. Participants experiencing distressing dreams or other sleep interference will be instructed to remove the patch before bedtime. If a severe skin reaction develops, the participant will be instructed to discontinue patch use. Use of the patch should reduce the severity of withdrawal-related symptoms. Withdrawal symptoms are generally short-lived and typically last no more than 2 weeks after smoking cessation. Patches will be dispensed under the supervision of a health care provider.

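### Section N promises continual risk monitoring, but no scheduled assessment in either arm asks about adverse events: patch reactions must be volunteered, and admissions may surface at week 12 by routes not tied to safety reporting

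*Combined protocol and SAP*

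**What the plan says.** Section N, under Serious adverse events, states: "Risks of participation will be continually monitored and appropriate measures implemented in cases of unforeseen adverse events". Its definition of a serious event includes death and "inpatient hospitalization or prolongation of existing hospitalization". On scope it says: "These events will be reported regardless of whether they appear to be related to study procedures". Unanticipated problems go to both IRBs within five business days of being discovered.

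Section K2 lists instructions for patch users. Some are triggered by a reaction, for example: "Those who experience a skin reaction from nicotine patch use will be instructed to move the site". It also says participants may contact staff with concerns.

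Section D, Measures, places the two primary assessments at baseline and 12 weeks. Between them the planned contact is a weekly app assessment. In the intervention arm, "AT participants will receive 6 PBM-based smoking-related questions". In the control arm, "we will ask SC participants to complete a weekly 6-item diet EMA". The Table of trial assessments has no row for adverse events or patch side effects. It does list the "Wisconsin Smoking Withdrawal Scale", a distress scale and a comorbidity measure at baseline and week 12, and an open-text app entry that the participant starts. Section E adds a medical-record review at baseline and 3 months, for tailoring the AT content.

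**The concern.** Monitoring, reporting and reaction-triggered advice all require that staff learn of the event. The five-day clock itself starts at discovery. Responsibility is assigned and the reporting duty is clear, but no form, question, look-back period or schedule is given for finding events.

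Two things are at stake. The first is safety: a participant with a patch reaction, or a cancer patient who is admitted, may not come to the team's notice while action is still useful. The second is interpretation: a report of few or no adverse events could reflect few events or few volunteers, and the data would not show which.

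**Working it through.** The plan states no figure on this point, so the check is a comparison of sections plus simple timing.

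**1. Every route by which staff could learn of an event**

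| Route (source) | When | Patch reaction | Hospital admission |
|---|---|---|---|
| Weekly app items (Section D, Measures) | Weekly | Not asked: smoking items in AT, diet items in SC | Not asked |
| Open-text app entry (Table) | Participant-initiated | If volunteered | If volunteered |
| Contact with staff (Section K2) | Participant-initiated | If volunteered | If volunteered |
| Withdrawal, distress and affect scales (Table) | Baseline, week 12; brief distress and affect items weekly | Not described as covering it | No |
| Comorbidity measure (Table, citing references 61 and 62) | Baseline, week 12 | Not described as covering it | Possible: reference 62 is a hospital-utilization questionnaire, but the items used are not listed |
| Chart review (Section E) | Baseline, 3 months | Not described as covering it | Possible: records recent diagnoses and medications |

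The weekly distress and affect items appear to belong to the smoking-related set that AT receives. Distress could then surface weekly in AT but not in SC.

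The Table also marks expired carbon monoxide in its weekly column. That column is defined as app-delivered, and Measures puts the breath test at the two primary assessments, so I do not count it as a weekly staff contact. If it were one, it would still carry no adverse-event question.

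**2. Timing of patch use against the next scheduled staff contact**

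Inputs from Section D: 2-week supply = 14 days; quit date = day 14; follow-up = 12 × 7 = day 84. The patch start day is not stated, so two assumptions are shown.

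- Start at enrollment: supply ends on day 0 + 14 = 14; gap = 84 − 14 = 70 days.
- Start on the quit date: supply ends on day 14 + 14 = 28; gap = 84 − 28 = 56 days.

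Either way, no scheduled contact during or soon after patch use is described as asking about the patch.

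**3. What a zero count would mean (illustration)**

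Both arms receive patches, so n = 80. With complete ascertainment and no reactions seen, the one-sided 95% upper bound on the reaction rate is 1 − 0.05^(1/80) = 3.7%. If only a fraction c of reactions is volunteered, the bound becomes 3.675% / c:

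- c = 0.5: 3.675 / 0.5 = 7.4%.
- c = 0.25: 3.675 / 0.25 = 14.7%.

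The documents give no value for c; these are assumptions. Under the present plan c cannot be estimated.

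**4. Participants who miss week 12**

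Both admission routes are set at the week-12 visit. Sections D and M count missing outcomes as smoking, and no step is described to find out why someone did not return. A death or a current admission could therefore appear in the data only as a non-abstinent outcome. Half the planned sample (40 of 80) are cancer survivors.

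**The case against.** The strongest reply is that ascertainment is better than a bare reading of the Table suggests. Several points stand, and they limit what can be claimed.

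- **Admissions.** A reader might infer that these too are captured only if volunteered. The documents do not support that: the week-12 comorbidity measure cites a hospital-utilization source, and charts are reviewed in both arms. What remains is that neither route is tied to serious adverse event reporting, and both come late. Caregivers may also have no chart at the study hospitals (an assumption).
- **Patch advice.** A reader might infer that participants get no usable advice before week 12. That is not supported either. Section N has warnings about smoking on the patch given at every dispensing, Section K2 has a health care provider supervising dispensing, and several K2 instructions can be given in advance. The gap concerns advice that depends on knowing a reaction has occurred.
- **No adverse experience is asked about at all.** This also goes too far. The plan treats withdrawal effects as adverse experiences, and withdrawal and distress are measured at week 12.
- **Biased safety comparison.** No between-arm safety analysis is planned, and both arms get the same patch supply, app training and, as far as the Table shows, open-text entry. Differential volunteering is possible but not shown.
- **Expected admissions.** The documents give no admission rate for these patients, so no expected count is claimed.

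Two further replies carry less weight. Section N defers to the IRBs' policies, but as described these govern monitoring and reporting and supply no question to participants. Consent pages and a few others were not available for this review, so the finding is limited to the text that was.

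**Conclusion.** The point holds in this form. The plan promises continual monitoring and cause-blind reporting of serious events, but no scheduled assessment in either arm is described as asking about adverse events. Skin, nausea and sleep reactions to the patch rely on the participant volunteering them, with 56 to 70 days between the end of the supply and the next scheduled staff contact, under the two assumed start days. Admissions may be found at week 12, but late, only in those who return, and without a stated link to safety reporting.

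The number of events missed cannot be estimated from the documents. This is a minimal-risk pilot, and the gap does not affect the primary efficacy comparison, except that an undetected death or admission may be counted as smoking. The change is worth making because it alters what is collected and costs little.

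**What to change.** 1. **Week-12 REDCap form, both arms:** add a short standard section on adverse events, patch problems and hospital stays since enrollment.
2. **Missed visits:** record vital status and reason for non-return. A self-report item cannot capture deaths.
3. **Link to reporting:** state that any admission found in the comorbidity items, chart review or new section goes to serious adverse event reporting under Section N.
4. **Weekly Insight assessment, both arms:** add one identical item on new health or patch problems, with positive replies flagged to the site team.
5. **Reporting:** give counts by arm descriptively, with the source of each event.

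No extra visit is needed. The costs are one more weekly item, one form section, follow-up of those who miss week 12, and flagged replies for existing site staff to read. Insight data go to the US institution's servers when a connection is available, so the flag needs a defined path back to the Lao team, and some replies will arrive with delay.
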